## 12.4. Appendix 4: Adverse Events: Definitions and Procedures for Recording, Evaluating, Follow-up, and Reporting

### Definition of AE

AE Definition

• An AE is any untoward medical occurrence in a clinical study participant, temporally associated with the use of a study treatment, whether or not considered related to the study treatment.

• NOTE: An AE can therefore be any unfavorable and unintended sign (including an abnormal laboratory finding), symptom, or disease (new or exacerbated) temporally associated with the use of a study treatment.

### Events Meeting the AE Definition

- Any abnormal laboratory test results (hematology, clinical chemistry, or urinalysis) or other safety assessments (eg, ECG, radiological scans, vital signs measurements), including those that worsen from baseline, considered clinically significant in the medical and scientific judgment of the investigator (ie, not related to progression of underlying disease).
- Exacerbation of a chronic or intermittent pre-existing condition including either an increase in frequency and/or intensity of the condition.
- New conditions detected or diagnosed after study treatment administration even though it may have been present before the start of the study.
- Signs, symptoms, or the clinical sequelae of a suspected drug-drug interaction.
- Signs, symptoms, or the clinical sequelae of a suspected overdose of either study treatment or a concomitant medication. Overdose per se will not be reported as an AE/SAE unless it is an intentional overdose taken with possible suicidal/self-harming intent. Such overdoses should be reported regardless of sequelae.

### Events NOT Meeting the AE Definition

- Any clinically significant abnormal laboratory findings or other abnormal safety assessments which are associated with the underlying disease, unless judged by the investigator to be more severe than expected for the participant's condition.
- The disease/disorder being studied or expected progression, signs, or symptoms of the disease/disorder being studied, unless more severe than expected for the participant's condition.
- Medical or surgical procedure (eg, endoscopy, appendectomy): the condition that

leads to the procedure is the AE.

- Situations in which an untoward medical occurrence did not occur (social and/or convenience admission to a hospital).
- Anticipated day-to-day fluctuations of pre-existing disease(s) or condition(s) present or detected at the start of the study that do not worsen.

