### 3.3.1. Risk Assessment

Potential Risk of Clinical Significance	Summary of Data/Rationale for Risk	Mitigation Strategy
Investigational Product (IP) [GSK3008348]		
Potential local irritancy	
Non-clinical:
 
Upper respiratory tract irritancy was observed in the 4-week inhalation toxicity studies in rats and dogs. Principal changes included epiglottic cartilage necrosis, regeneration/remodelling at 5850 and 12000 µg/kg/day in rats; and soft palate or laryngeal ulcerations in dogs at 3070 and 8710 µg/kg/day. No Observed Adverse Effect Levels (NOAELs) were identified at the lowest doses tested (1420 and 899 µg/kg/day in rats and dogs, respectively).
 
Lower respiratory tract irritancy was also observed in the 4-week inhalation toxicity study in dogs. Adverse mixed inflammation and alveolar macrophage aggregates were observed at 3070 and 8710 µg/kg/day. These findings were also present in some animals from the lowest dose tested (899 µg/kg/day – the NOAEL), including control. Changes in local draining lymph nodes of GSK3008348-treated dogs were considered to be a non-adverse secondary response to the pulmonary inflammation.
 
Non-adverse alveolar macrophage aggregates were seen at a low incidence in the lungs of all treated groups and also in control males in the 4-week inhalation study in rats. A minor test article-related effect could not be entirely discounted in female rats.
	
In this planned first-time-in-patient study, IPF patients will only receive single doses.
 
Appropriate inclusion/exclusion criteria (e.g., exclusion for current upper or lower respiratory tract infection) will be implemented in clinical protocols.
 
Potential adverse events associated with irritancy (e.g., sore throat, cough, dyspnoea, wheezing) are readily monitored, and will be monitored during the study. Interpretation of these AEs may be compromised in IPF patients where cough or dyspnoea may be symptoms of their respiratory diseases. Therefore patients' baseline symptoms will be recorded as part of the current conditions assessment, and physical measurements including respiratory rate and oxygen saturation monitoring reviewed, to aid interpretation of any new symptoms. It is anticipated that symptoms secondary to irritancy will be more acute in nature, which will help distinguish from chronic symptoms due to IPF.
 
Symptoms of clinical concern may be investigated further in collaboration with an Ear, Nose and Throat

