## 5.4. Scientific Rationale for Study Design

- Cohort 1 includes a placebo control to allow assessment of safety and tolerability, as reporting of adverse events in patients receiving placebo will facilitate the differentiation between ‘disease’ and ‘intervention’ adverse events.
- Cohort 1 will be conducted in a double-blind (sponsor unblind) fashion. Safety and PK data reviews will be conducted without treatment group assignment or subject numbers, so that the investigators and data review team remain blinded. The

statistician will perform an unblinded review of PET data as part of the pre-planned interim analysis, to allow appropriate decision-making. The sponsor (including the medical monitor) may also undertake separate in-stream review of unblinded data to help determine the most appropriate response to emerging data.

- The number of patients to be enrolled in Cohort 1 (7 participants) is based on the probability of detecting a change in  $\alpha\beta 6$  internalisation at approximately 30 min post-dose compared to pre-dose of 6% or greater, as measured by the uptake of [F]-FBA-A20FMDV2 in the lungs reported as the volume of distribution [VT]. This predetermined change is equivalent to approximately half the difference in [F]-FBA-A20FMDV2 PET signal observed between healthy volunteers and IPF patients in a previous study RES116235. If GSK3008348 cannot achieve that reduction in  $\alpha\beta 6$ -associated PET signal and the endpoint variability is as expected, then the study will end.
- The design for Cohort 2 will be defined following completion of Cohort 1, to ensure the most informative doses of GSK3008348 are selected and the PET scans are timed appropriately. Cohort 2 data may be reviewed in-stream and the design of Cohort 2 adjusted to maximise the value of the data obtained. The aim is to assess target engagement while exposing the smallest possible number of patients to ionising radiation from the PET procedure.

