### 8.1.3. Individual Adverse Event Stopping Criteria

A participant will be withdrawn from the study if they experience:

1. An SAE that is at least possibly related to the study treatment
2. An IPF exacerbation, upper or lower respiratory tract infection or other systemic infection
3. A clinically significant change in a laboratory value or vital sign
4. Failure to recover from an adverse event

A participant can be discontinued from therapy if the investigator decides that the patient should be withdrawn.

Participants who are withdrawn will complete the follow-up visit, as described in the SoA.

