## Definition of SAE

If an event is not an AE per definition above, then it cannot be an SAE even if serious conditions are met (eg, hospitalization for signs/symptoms of the disease under study, death due to progression of disease).

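### Appendix 4 lets expected IPF symptoms be left out of the AE data without defining what is expected, which conflicts with its own rule on worsening and with the stated reason for the placebo arm

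*Protocol*

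**What the plan says.** Safety and tolerability is a primary objective (protocol section 4).

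- **Exclusion.** Appendix 4, under events not meeting the AE definition, lists "The disease/disorder being studied or expected progression, signs, or symptoms of the disease/disorder being studied, unless more severe than expected", judged against the participant's condition.
- **Carry-over to SAEs.** The SAE definition adds: "If an event is not an AE per definition above, then it cannot be an SAE even if serious conditions are met". Its examples are hospitalisation for symptoms of the disease under study and death from its progression.
- **Inclusion.** The same appendix, under events that do meet the definition, lists "Exacerbation of a chronic or intermittent pre-existing condition including either an increase in frequency and/or intensity of the condition". The general definition covers new or exacerbated symptoms whatever their relation to treatment.
- **Stopping criteria.** Section 8.1.3, whose heading concerns individual adverse events, includes "An IPF exacerbation, upper or lower respiratory tract infection or other systemic infection".
- **Purpose of placebo.** Section 5.4 says that "reporting of adverse events in patients receiving placebo will facilitate the differentiation between" disease events and events due to the intervention.
- **Drug risk.** Section 3.3.1 has one row for the investigational product, potential local irritancy, which may present as sore throat, cough, dyspnoea or wheezing. It concedes: "Interpretation of these AEs may be compromised in IPF patients where cough or dyspnoea may be symptoms of their respiratory diseases". As mitigation it plans to record baseline symptoms and to review respiratory rate and oxygen saturation.

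**The concern.** Section 5.4 makes sense only if disease events enter the AE data in both arms, so that the placebo participants show the background. Appendix 4 allows that sorting to happen earlier, one event at a time: an investigator who judges a cough or breathlessness to be expected IPF need not record it. The symptoms most open to this judgement are the two that section 3.3.1 names as overlapping with the drug's potential irritancy.

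What is at stake is the reading of the AE tables. A table with little or no cough and dyspnoea could mean that there was no irritancy, or that such events were classed as IPF and never recorded. The tables would not tell these apart.

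**Working it through.** The point concerns a definition, and the plan has no figure to reproduce. The check sets the rules side by side, looks at what else would catch the events, and then gives a scale.

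**1. The rules applied to the same event**

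| Event after first dose | General definition and inclusion list | Exclusion list | Outcome |
|---|---|---|---|
| Baseline cough, no worse | Not an AE | Not an AE | Consistent |
| Symptom worse than expected for this participant | AE | Exemption does not apply | Consistent: AE |
| Baseline cough, now more frequent, but within what is expected in IPF | AE, because frequency rose | Not an AE | Contradiction |
| Cough or dyspnoea new to this participant | AE, whatever the cause | Not an AE if judged an expected IPF symptom | Left to judgement |
| IPF exacerbation | AE, and treated as one by the heading of 8.1.3 | Depends on whether it exceeds what is expected | Left open |
| Hospitalisation for IPF symptoms | Meets a seriousness criterion | Not an SAE if the symptom is not an AE | Follows the judgement above |

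The conflict lies in the comparator. The inclusion list compares with the participant's previous state; the exclusion list compares with what is expected in the disease. The two diverge when a symptom worsens but stays within expectation.

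**2. What else would catch such events** (protocol section 2 and SAP Appendix 2 for the schedule; SAP Appendix 12 for displays)

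- *FEV1 and FVC:* measured at 1 h and 24 h in dosing period 1. In period 2 they are measured before dosing and then not until follow-up.
- *Oxygen saturation:* continuous to 4 h on Day 1 of period 1 only.
- *Vital signs, including respiratory rate:* both periods.
- *Symptoms:* current conditions are recorded at screening and before the first dose. No symptom instrument is scheduled later, so later symptoms reach the analysis mainly through AE review.
- *Spirometry falls as AEs:* section 9.4.6 makes clinically significant falls AEs. However, Appendix 4 ties clinical significance of safety assessments to their not reflecting progression of underlying disease, so the same filter can apply.
- *Withdrawals and deaths:* SAP Listing 2 gives reasons for withdrawal, and section 9.2.5 captures all deaths on a separate form.
- *Displays:* the SAP plans lung function tables and figures and a saturation listing, but no respiratory-symptom display outside AEs.

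**3. Scale, under assumed rates**

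Let p be the chance that an active participant has a respiratory reaction, and f the fraction of reactions classed as expected IPF and not recorded. With 5 active participants (section 5.1.1), P(no recorded event) = (1 − p(1 − f))^5.

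| p | f = 0 | f = 0.25 | f = 0.5 |
|---|---|---|---|
| 0.1 | 0.9^5 = 0.59 | 0.925^5 = 0.68 | 0.95^5 = 0.77 |
| 0.3 | 0.7^5 = 0.17 | 0.775^5 = 0.28 | 0.85^5 = 0.44 |
| 0.5 | 0.5^5 = 0.03 | 0.625^5 = 0.10 | 0.75^5 = 0.24 |

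Both p and f are assumptions; the documents give neither. The table covers the active arm only.

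For placebo, with 2 participants and a background symptom rate q, P(no event) = (1 − q)^2: 0.81, 0.64, 0.49 and 0.25 for assumed q of 0.1, 0.2, 0.3 and 0.5. Even the most extreme split, 5/5 against 0/2, has a Fisher exact p of 1/21 = 0.048; 4/5 against 0/2 gives 3/21 = 0.14. SAP section 2.4 plans no formal safety comparison, so these figures only show how little information there is.

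**The case against.** The strongest reply is that the exemption is narrow and much is caught elsewhere. It covers only expected symptoms that are no more severe than expected. The general definition includes new or exacerbated symptoms, the inclusion list covers increased frequency or intensity, and the bullet on day-to-day fluctuation exempts only what does not worsen. Irritancy is expected to be more acute than chronic IPF symptoms. Lung function, saturation, vital signs and oropharyngeal examination do not depend on AE terms. With 2 placebo participants the comparison is weak even with complete recording.

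Much of this stands and limits the point. Four stronger readings are tempting, and the documents do not support them:

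- *All IPF symptoms are excluded from AEs.* The qualifier on severity rules this out.
- *A participant withdrawn for an exacerbation could vanish from the report.* Listing 2 would show the withdrawal. Section 8.1.3 and the inclusion list, read together, also favour recording an AE. What is uncertain is only whether it appears in the AE displays.
- *Irritancy is an established risk that mimics IPF throughout.* The protocol calls it potential and bases it on animal findings; no upper respiratory irritancy was seen in healthy volunteers. It states the overlap for cough and dyspnoea, not for sore throat or wheezing.
- *The disease exemption should be abolished for respiratory events.* That is a debatable safety-reporting policy, and resolving the conflict does not need it.

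The reply does not remove the contradiction. The provisions that favour recording sit beside one that permits omission, and nothing says which prevails. The objective measures thin out in dosing period 2.

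**Conclusion.** The point holds in limited form. Appendix 4 contradicts itself on a symptom that worsens within what is expected. It leaves the AE status of an IPF exacerbation open although section 8.1.3 treats it as an adverse event. It also permits sorting by presumed cause before the placebo data that section 5.4 relies on are collected. Post-dose cough and dyspnoea are the symptoms exposed, with partial cover from other measures, better in period 1 than in period 2.

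The size cannot be estimated. The direction is clear: any omission makes an empty AE table more likely. The amount depends on p and f, which are assumed above, so no single cell of that table should be quoted as an estimate. The change is worth making because it affects the data behind a primary objective and costs little. It would not turn 5 against 2 participants into a strong comparison.

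**What to change.** Reconcile these passages with one study-specific paragraph in Appendix 4:

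- From first dose to follow-up, in both arms, any respiratory sign or symptom that is new or worse than the recorded baseline symptoms, including IPF exacerbation, is recorded as an AE whatever its suspected cause.
- Attribution to IPF is made in the causality assessment, where Appendix 4 already asks investigators to weigh underlying disease.
- The exemption stays for stable, expected IPF symptoms that do not worsen.
- The SAE paragraph is aligned so that events recorded as AEs under this rule are assessed for seriousness in the usual way.

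This concerns recording only and leaves the withdrawal criteria in section 8.1.3 as they are. It costs a paragraph, matching CRF guidance and a few extra AE records reflecting background IPF, in a cohort planned at 7.

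SAP section 1.1 reports that the study ended after Cohort 1, so new wording can help only where data are still to be recorded. For data already collected, the study report should state the recording rule beside the AE tables and read them together with lung function, saturation, vital signs and Listing 2.

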## Definition of SAE

If an event is not an AE per definition above, then it cannot be an SAE even if serious conditions are met (eg, hospitalization for signs/symptoms of the disease under study, death due to progression of disease).

### A SAE is defined as any untoward medical occurrence that, at any dose:

#### a. Results in death

#### b. Is life-threatening

The term 'life-threatening' in the definition of 'serious' refers to an event in which the participant was at risk of death at the time of the event. It does not refer to an event, which hypothetically might have caused death, if it were more severe.

#### c. Requires inpatient hospitalization or prolongation of existing hospitalization

In general, hospitalization signifies that the participant has been detained (usually involving at least an overnight stay) at the hospital or emergency ward for observation and/or treatment that would not have been appropriate in the physician's office or outpatient setting. Complications that occur during hospitalization are AE. If a complication prolongs hospitalization or fulfills any other serious criteria, the event is serious. When in doubt as to whether "hospitalization" occurred or was necessary, the AE should be considered serious.

Hospitalization for elective treatment of a pre-existing condition that did not worsen from baseline is not considered an AE.

#### d. Results in persistent disability/incapacity

- The term disability means a substantial disruption of a person's ability to conduct normal life functions.
- This definition is not intended to include experiences of relatively minor medical significance such as uncomplicated headache, nausea, vomiting, diarrhea, influenza, and accidental trauma (eg, sprained ankle) which may interfere with or prevent everyday life functions but do not constitute a substantial disruption.

#### e. Is a congenital anomaly/birth defect

#### f. Other situations:

- Medical or scientific judgment should be exercised in deciding whether SAE reporting is appropriate in other situations such as important medical events that may

not be immediately life-threatening or result in death or hospitalization but may jeopardize the participant or may require medical or surgical intervention to prevent one of the other outcomes listed in the above definition. These events should usually be considered serious.

Examples of such events include invasive or malignant cancers, intensive treatment in an emergency room or at home for allergic bronchospasm, blood dyscrasias or convulsions that do not result in hospitalization, or development of drug dependency or drug abuse.

## Recording AE and SAE

AE and SAE Recording

When an AE/SAE occurs, it is the responsibility of the investigator to review all documentation (eg, hospital progress notes, laboratory, and diagnostics reports) related to the event.

The investigator will then record all relevant AE/SAE information in the eCRF.

It is not acceptable for the investigator to send photocopies of the participant's medical records to GSK in lieu of completion of the GSK /AE/SAE eCRF page.

There may be instances when copies of medical records for certain cases are requested by GSK. In this case, all participant identifiers, with the exception of the participant number, will be redacted on the copies of the medical records before submission to GSK.

The investigator will attempt to establish a diagnosis of the event based on signs, symptoms, and/or other clinical information. Whenever possible, the diagnosis (not the individual signs/symptoms) will be documented as the AE/SAE.

Assessment of Intensity

The investigator will make an assessment of intensity for each AE and SAE reported during the study and assign it to 1 of the following categories:
 

Mild: An event that is easily tolerated by the participant, causing minimal discomfort and not interfering with everyday activities.

Moderate: An event that causes sufficiently discomfort and interferes with normal everyday activities.

Severe: An event that prevents normal everyday activities. An AE that is assessed as severe should not be confused with an SAE. Severe is a category utilized for rating the intensity of an event; and both AE and SAE can be assessed as severe.

 
An event is defined as 'serious' when it meets at least 1 of the predefined outcomes as described in the definition of an SAE, NOT when it is rated as severe.

### Assessment of Causality

- The investigator is obligated to assess the relationship between study treatment and each occurrence of each AE/SAE.
- A "reasonable possibility" of a relationship conveys that there are facts, evidence, and/or arguments to suggest a causal relationship, rather than a relationship cannot be ruled out.
- The investigator will use clinical judgment to determine the relationship.
- Alternative causes, such as underlying disease(s), concomitant therapy, and other risk factors, as well as the temporal relationship of the event to study treatment administration will be considered and investigated.
- The investigator will also consult the IB and/or Product Information, for marketed products, in his/her assessment.
- For each AE/SAE, the investigator **must** document in the medical notes that he/she has reviewed the AE/SAE and has provided an assessment of causality.
- There may be situations in which an SAE has occurred and the investigator has minimal information to include in the initial report to GSK. However, **it is very important that the investigator always make an assessment of causality for every event before the initial transmission of the SAE data to GSK.**
- The investigator may change his/her opinion of causality in light of follow-up information and send an SAE follow-up report with the updated causality assessment.
- The causality assessment is one of the criteria used when determining regulatory reporting requirements.

### Follow-up of AE and SAE

- The investigator is obligated to perform or arrange for the conduct of supplemental measurements and/or evaluations as medically indicated or as requested by GSK to elucidate the nature and/or causality of the AE or SAE as fully as possible. This may include additional laboratory tests or investigations, histopathological examinations, or consultation with other health care professionals.
- If a participant dies during participation in the study or during a recognized follow-up period, the investigator will provide GSK with a copy of any post-mortem findings including histopathology.
- New or updated information will be recorded in the originally completed eCRF.
- The investigator will submit any updated SAE data to GSK within 24 hours of receipt of the information.

